#### **Objectives**

- To describe patients, invasive procedures, infections, and antimicrobials prescribed.
- To estimate the prevalence of clinical isolates from ICU patients that are positive for carbapenemase-producing Enterobacterales.
- To estimate the prevalence of rectal screening isolates from ICU patients that are positive for carbapenemase-producing *Enterobacterales*.
- To understand patient characteristics, procedures, and antimicrobial use which are associated with CPE colonisation or infection
- To understand inequalities in the prevalence of CPE colonisation and infection.
- To raise awareness of the growing concern of CPE in ICU patients.

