# Study design

A prospective, cluster randomised cross-sectional survey approach will be used to provide estimates of prevalence of CPE for clinically indicated samples and rectal screening (stool sample or rectal swab) isolates from the randomly selected acute trusts.

Samples taken for routine clinical management purposes from the selected patients (e.g. blood, urine, wound) will be included, as will rectal screening (stool sample or rectal swab) taken to determine if the patient is colonised with a CPE.

The selected patients receiving in-patient treatment in the participating trusts' units will be included in the survey on the survey date. A single survey day will be used for each trust to minimise the workload for the clinical teams and to optimise sample collection.

Intensive care ward staff will implement the survey by randomly selecting patients and providing relevant data for the survey. To ease the workload, an online survey tool will be used for data collection purposes. ICU staff will be advised on methods of randomly selecting patients within the ward; the method by which patients are selected will be dictated by the number of critical care beds.

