# Data collection

Data collection from patient records will be carried out by hospital staff, using a digital data collection system, adapted from the HCAI Data Capture System (DCS) used for ICCQIP and the mandatory surveillance of healthcare associated infections. Some additional data will be collected through linkage to Hospital Episodes Statistics. It is anticipated that the data collection will primarily be done by staff on the ward being surveyed, but it is also possible that infection prevention and control could also be brought in to assist with the survey process.

 Patients are recruited from a single day. However, there will be two weeks available following the study date for trusts to enter the data.

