# **Data analysis**

For hospital, ward and patient demographic variables, descriptive and summary statistics will be presented. CPE prevalence estimates will be calculated overall and also presented by strata. Associations between colonisation or infection with CPE and hypothesised risk factors data will also be analysed using univariable, and if required, multivariable analysis. Results will be stratified by ICU-type, with odds ratios, p-values and 95% CI. All analysis will be done using Stata 15.1.

Anonymised results from the survey may be used to inform additional CPE/CPO assessments to understand the impacts of AMR in line with the National Action Plan.

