#### The following data will be collected once per patient

The following data should be answered in relation to the date as referenced in the list below.

Note only one date is required, please complete for the first that is applicable as working down the list

- 1. Date of screening test (if single test)
- 2. If multiple screening tests:
  - a. If any positive, date of first positive screen OR
  - b. If all negative, date of most recent screen
- 3. Today's date if never screened

Field name	Field description	Response/notes				
Patient details						
Patient ID	Unique patient ID	System generated				
*Reporting organisation	ICU name	Single select drop down				
*Date of interest	Date of interest to which exposure questions relate. In order of preference:	DD-MM-YYYY				
	1. Date of CPE screening test (if single test) 2. If multiple CPE screening tests: a. If any positive, date of first positive screen OR b. If all negative, date of most recent screen					
	3. Today's date if never screened					
*10-digit NHS number	10-digit NHS number, if not available, enter [contact]					
*Forename	Patient first name	Text				
*Surname	Patient surname	Text				
*Date of birth	Patient date of birth	DD-MM-YYYY, if not known enter 01/01/1900				
*Sex	Biological sex	Button options:				
		Male Female Unknown				
Patient details 2						
*Survey date	Date survey is conducted	DD-MM-YYYY				
*Patient age group		Single select drop-down: Adults				
		Paediatrics				
		Neonates				

Ethnicity	Ethnicity of patient	Two-stage single select drop-down
*UK resident	Indicate if patient normally resides in the UK  NB. If for a neonate, please use details of mother	Single select drop-down: Yes No Unknown
Normal country of residence if not UK		Single select drop-down
*Birthweight	Birth weight (in grams) of neonatal patients i.e. babies less than 28 days old OR on NICU.	Number in grams
*Gestation	Gestation for babies aged under 1 year	Weeks + days
*Patient category	Indicate patient category on admission	Single select drop-down: NHS Private Diplomatic Other Unknown
Other patient category	Specify patient category if "other"	Text
*Date admitted to hospital	Date admitted to the trust, or date of birth if neonate and admitted since birth	DD-MM-YYYY
*Admitted from	Setting patient admitted from into the trust	Single select drop-down:  Home  A&E International transfer Nursing home Other Trust  Non-NHS hospital Non-health-related institute Temporary accommodation Other

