Indicate which carbapenemase family was detected (select all that apply)	Indicate which carbapenemase family was detected (select all that apply)	Multiselect drop-down
If Other, specify other carbapenemase family		Text
Screening (NB no additional sc	reening is required)	
*CPE on admission to Trust	Was the patient known to be CPE positive on admission to Trust	Single select drop-down: Yes – colonised Yes - infected No Unknown
*CPE screening on admission to Trust	Found to be CPE positive on admission to Trust.  "Yes" if screening specimen positive, "no" if screening specimen negative, "unknown" if no screen performed.	Single select drop-down: Yes No Unknown
*CPE on admission to ICU	Known to be CPE positive on this admission to ICU i.e. communicated/identified at time of admission.	Single select drop-down: Yes No Unknown
*ICU screen required	Did patient meet requirement to be screened for CPE on ICU in accordance with your policy?	Single select drop-down: Yes No Unknown
*ICU admission screen	Was patient screened for CPE on this admission to ICU?	Single select drop-down: Yes No Unknown

		1
*ICU admission screen date	Date admission screen was taken on ICU	DD-MM-YYYY
*Result of ICU admission screen	Indicate result from ICU CPE admission screen	Single select drop-down: Positive Negative Unknown
*Previous CPE	Indicate if patient known to be CPE colonised/infected in 12 months prior to first day of survey	Single select drop-down: Yes – colonised Yes - infected No Unknown
If previous history of CPE, specify date of most recent positive result.	Provide date of most recent CPE positive result (prior to ICU admission screen, if taken)	DD-MM-YYYY
Previous contact with CPE	Indicate if in contact with known CPE case during this admission	Single select drop-down: Yes No Unknown
Healthcare exposure		
*UK non-NHS hospital admission in previous 12 months	Any hospital admissions to non-NHS hospitals in the previous 12 months	Single select drop-down: Yes No Unknown
Specify UK non-NHS hospital admission	Provide name(s) of non- NHS hospitals admitted to in previous 12 months	Free text
*Healthcare overseas in previous 12 months	Any hospital admissions overseas in 12 months prior to admission at Trust	Single select drop-down: Yes No Unknown
Specify healthcare abroad	List countries where overseas healthcare received in previous 12 months	Multiselect dropdown of countries

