weeks prior to the date of interest?	the four weeks prior to the date of interest	No Unknown
If yes, which?	Carbapenems	Multiselect drop-down Doripenem Ertapenem Faropenem
		Imipenem
		Imipenem with cilastin Imipenem with cilastin and relebactam
		Meropenem  Meropenem/vaborabactam
*Has the patient received carbapenems in the one year prior to the date of interest, but not in the four weeks prior?		Single select drop-down: Yes No Unknown
If yes, which	Carbapenems	Multiselect drop-down
*Has the patient received 3rd generation cephalosporins in the four weeks prior to the date of interest?		Single select drop-down: Yes No Unknown
If yes, which	3rd generation cephalosporins	Multiselect drop-down
*Has the patient received 3rd generation cephalosporins in the one year prior to the date of interest, but not in the four weeks prior		Single select drop-down: Yes No Unknown
If yes, which	3rd generation cephalosporins	Multiselect drop-down
*Antimicrobials prescribed and taken on the date of interest	Indicate if the patient has received at least one	Single select drop-down:

	systemic antibiotic on the date of interest (given or planned treatment, including intermittent treatments, e.g. alternate day or medical prophylaxis). For surgical prophylaxis, check whether any surgical prophylaxis was given in the 24 hours before 8 a.m. on the day of the survey. If "yes", collect antibiotic data.	Yes No Unknown
Please select the number of antimicrobials taken		Single select drop-down:  1  2  3  4  5
*Antimicrobial name 1-5  NOTE: Field repeated up to 5 times depending on the specified number of antimicrobials taken	Select which antimicrobial	Single-select dropdown list of antimicrobials.
*Antimicrobial indication 1-5  NOTE: Field repeated up to 5 times depending on the specified number of antimicrobials taken	Please give indication for this/these antimicrobial(s)	CI = treatment of community-acquired infection LI = treatment of infection acquired in long-term care facility (e.g. nursing home) HI = treatment for acute hospital-acquired infection SP = surgical prophylaxis MP = medical prophylaxis O = other indication UI = unknown indication (confirmed) UNK = unknown or missing information

	T	T
*CPE indication for antimicrobial 1-5  NOTE: Field repeated up to 5 times depending on the specified number of antimicrobials taken	Is this antibiotic prescribed to manage CPE?	Single select drop-down: Yes No Unknown

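### The date of interest is set by screening tests alone, so exposures of clinically detected CPE cases are read at the wrong date

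*Protocol*

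**What the plan says.** The protocol's Objectives include: "To understand patient characteristics, procedures, and antimicrobial use which are associated with CPE colonisation or infection". Study design brings in clinical specimens as well as rectal screens: "Samples taken for routine clinical management purposes from the selected patients (e.g. blood, urine, wound) will be included". Data analysis pools the two: "Associations between colonisation or infection with CPE and hypothesised risk factors data will also be analysed using univariable", with multivariable models if required. It does not list the risk factors.

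In Appendix 1, under the data collected once per patient, the date of interest is described as "Date of interest to which exposure questions relate". The order of preference begins with "Date of CPE screening test (if single test"). With several screens it is the first positive screen, or the most recent screen if all are negative. A patient never screened gets the date of the day. A separate mandatory field holds the survey date.

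Three other items bear on this:
- Previous CPE: "Indicate if patient known to be CPE colonised/infected in 12 months prior to first day of survey".
- The item on antimicrobials on the date of interest includes a check whether "surgical prophylaxis was given in the 24 hours before 8 a.m. on the day of the survey".
- A footnote to Data collection says "there will be two weeks available following the study date for trusts to enter the data".

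**The concern.** A risk-factor analysis needs exposures that precede the outcome. The outcome here can be established by a blood, urine or wound specimen, but the date that separates before from after can only be a screening date. Screening cannot be read loosely to cover both, because the microbiology section of the same form asks whether the specimen was screening or clinical.

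For clinically detected cases, drugs, lines, surgery or endoscopy that followed the infection may be reported as associated with acquiring it, or real earlier exposures may be lost. Most of the affected answers are given on the form against that date, so a later analysis plan can undo only part of the error.

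**Working it through.** **1. The rule traced through patient histories**

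| History in this admission | Date of interest | Consequence |
|---|---|---|
| First positive is a screen | That screen | Correct |
| Clinical positive, never screened | Day of completion | Treatment after the specimen can count as prior exposure |
| Clinical positive, screened only later | The later screen | Same error, for the interval between the two |
| Negative screen, later clinical positive, no further screen | The negative screen | Exposures between screen and infection are missed |

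**2. Fields that depend on it.** Surgery and endoscopy are asked up to the date of interest. Devices are asked as in place on it, or shortly before. Carbapenems and third-generation cephalosporins are asked for the four weeks before it and for the rest of the preceding year.

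**3. What could be corrected afterwards.** The form has mandatory surgery and endoscopy dates, optional device dates, a mandatory specimen date, and a mandatory question whether each itemised antimicrobial (up to five) was given to manage CPE. Linkage to the Second Generation Surveillance System is anticipated. The limits are:
- The carbapenem and cephalosporin yes/no items are mandatory but carry neither a date nor the CPE-indication question, so they cannot be re-windowed.
- The specimen date is the most recent one when there are several, not the first positive.
- Only the most recent surgery and endoscopy are recorded, so removing a later one can hide an earlier one.

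**4. Size.** The protocol gives no figure for this, and all three inputs below are assumptions. Let e0 be exposure in controls and exposure of cases before the specimen, f the share of cases anchored after a clinical positive, and g the chance that an otherwise unexposed such case receives the drug between specimen and anchor. The true odds ratio is 1.

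e1 = e0 + (1 − e0)·f·g; OR = [e1/(1 − e1)] / [e0/(1 − e0)]

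With e0 = 0.20 (control odds 0.25):

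| g | f = 0.2 | f = 0.4 | f = 0.6 |
|---|---|---|---|
| 0.5 | e1 = 0.28, OR 1.56 | e1 = 0.36, OR 2.25 | e1 = 0.44, OR 3.14 |
| 0.1 | e1 = 0.216, OR 1.10 | e1 = 0.232, OR 1.21 | e1 = 0.248, OR 1.32 |

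A wider grid (e0 0.1 to 0.4, f 0.1 to 0.5, g 0.3 to 0.9) runs from 1.08 to 9.18. The largest value needs all three inputs at their extreme. The model covers only the second and third histories, not the missed exposures of the fourth.

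**5. Expected cases.** The protocol's largest sample sizes follow from n = 2·N·p(1 − p)/[(d/1.96)²(N − 1) + p(1 − p)], with N the number of beds, rounded up, multiplied by 1.1 and rounded up again:
- Adults (N = 4090, p = 1%, d = 1%): 696.06 → 697 → 767.
- Neonates (N = 1441, p = 1%, d = 1%): 602.12 → 603 → 664.
- Paediatrics (N = 312, p = 1%, d = 2%): 146.10 → 147 → 162.

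All three match. At 1% prevalence they yield 7.67, 6.64 and 1.62 cases, or about 8, 7 and 2.

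Suppose 2 of 8 adult cases are truly exposed (odds 2/6 = 0.33). One misdated case makes it 3 of 8 (odds 3/5 = 0.60) and multiplies the odds ratio by 1.8. Two make it 4 of 8 (odds 1.00) and multiply it by 3.

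**The case against.** The aim is prevalence, and neither prevalence objective uses the date of interest. Only the association objective is touched, and only for cases first detected clinically. This stands and sets the severity.

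The form already holds much of what is needed to re-order events, and an analysis plan that is not shown may use it. This stands in part: it does not reach the undated carbapenem and cephalosporin items.

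The odds ratios are soft. Never-screened controls are also anchored on the day of completion and accrue exposure. With control exposure at 25%, the values 1.56, 2.25 and 3.14 fall to 1.17, 1.69 and 2.36. The protocol's Background notes that carbapenemase destroys carbapenems, which argues for a low g for that class. Both points stand, which is why only a range is given.

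Some stronger readings are tempting, but the documents do not support them:
- *In trusts without screening every case is misclassified.* A case already exposed before the specimen, or untreated after it, is recorded correctly on that exposure.
- *Previous CPE makes the outcome its own predictor.* The protocol does not name it as a risk factor. Its optional companion date field asks for a positive before the ICU admission screen, which suggests that earlier history was meant. What holds is that the yes/no item lacks that bound and, read literally, can capture the index positive.
- *The anchor can fall two weeks after the survey.* The footnote concerns data entry, and a printable form allows completion first. What holds is that the wording is ambiguous beside a separate survey date.

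**Conclusion.** The date-of-interest rule has no branch for clinical specimens, although clinically detected infection is part of the outcome analysed. Cases detected that way can be anchored too late or too early, so the bias can run in either direction. Cases first found by screening are dated correctly.

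The size cannot be fixed from the documents. With 20% background exposure, 20% to 60% of cases anchored late, and 10% to 50% of the otherwise unexposed among them treated after the specimen, a null association appears as an odds ratio of about 1.1 to above 3. With about 8, 7 and 2 expected cases at 1% prevalence, one or two misdated cases can shape a result.

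Three secondary inconsistencies belong with it: Previous CPE is bounded by the first survey day; surgical prophylaxis is tied to the survey day inside a date-of-interest question; and the fallback date is not stated to be the survey date. This should be fixed before data collection. It does not threaten the prevalence estimates.

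**What to change.** In Appendix 1 and the user guide:

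1. Define the date of interest as the collection date of the first CPE-positive specimen of either type in this admission; if all are negative, the most recent CPE test; if never tested, the survey date. Change both the list at the head of the patient section and the table entry.
2. Record the collection date of the first positive specimen, instead of only the most recent specimen date, so that the anchor can be checked.
3. Limit Previous CPE to the time before this hospital admission.
4. End Previous contact with CPE, which now covers the admission without an end date, at the date of interest.
5. Align the recording window for surgical prophylaxis with the date of interest.

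The cost is the rewording of a few form items and the user guide, plus one specimen date for patients with several specimens. No extra sampling is needed and no sample size changes. In the illustration above, the spurious odds ratio returns to 1, because treatment after the first positive specimen no longer counts.

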#### Information collected

The survey will collect data on a number of broad topics. These include:

- Trust-level data
- ICU-level data
- Patient data
- Patient data (day of survey)
- Patient data (microbiology)

The majority of the survey will be filled in by ICU staff, but it is anticipated that some additional data not included in the survey can be provided via data linkage with other systems, including the Second Generation Surveillance System for microbiology results and Hospital Episodes Statistics for some patient data. All data that can be obtained via reliable data linkage has already been excluded from the Point Prevalence Survey questions. Data will be enriched using the NHS DBS.

Further details on the proposed questions to be included in the survey can be found in the appendix.

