Other admitted from	Specify if admitted from "other" location	Text

*Date admitted to ICU	Date admitted to ICU	DD-MM-YYYY
Time admitted to ICU	Specify time admitted to ICU	HH:MM (24-hour clock)
*Location admitted to ICU from	Setting patient admitted from into ICU	Single select drop-down: Home A&E HDU within same Trust Other ward within same Trust International transfer Nursing home Other Trust
		Non-NHS hospital Non-health-related institute Temporary accommodation Other Unknown
Other admitted from (ICU)	Specify if admitted to ICU from "other" location	Text
*If admitted to ICU from another ward within the same Trust, please specify	Specify specialty patient was admitted into the ICU from	Single select drop down Adult Paeds Neonates Other
If other, please specify	Specify other/specialty	Text
Please specify Adult speciality		
 
General medical
 
General surgical
 
Specialty
 
Intensive care
 

Please specify Paeds speciality		

Medical

Surgical

Specialty

Intensive care

		

Surgical

Specialty

	Γ	T
If 'Speciality', please specify which Paeds speciality	Specify other/specialty	Text
If 'Speciality', please specify which Neonatal speciality	Specify other/specialty	Text
APACHE II score	Score measures severity of disease for patients admitted to ICUs. Provide score assigned to patient on admission to ICU	Integer, ranging 0 - 71
Microbiology details		
*Was this patient tested for CPE, either as screening or as part of clinical investigations?		Single select drop-down: Yes No Unknown
*Was it a screening or clinical specimen?	Indicate if screening specimen or clinical specimen	Single select drop-down: Screening Clinical Unknown
*Date CPE specimen collected	Date specimen collected (if single specimen). If multiple specimens, please provide the most recent date.	DD-MM-YYYY
Specimen/laboratory number assigned to specimen		Free text
Indicate anatomical site specimen collected if clinical specimen		Single select drop-down
*Organism	Organism isolated associated with CPE positive result. If no result yet, select "Unknown/result awaited". If no organism isolated, select "No organism isolated".	Single select drop-down

	T	T
Does phenotypic testing indicate the presence of a carbapenemase?	Indicate if phenotypic (antibiotic susceptibility) testing indicates presence of a carbapenemase	Single select drop-down: Yes No Unknown

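### The Microbiology details block takes one specimen per patient, the most recent, while exposures are dated from the first positive screen, so positives can be displaced or mis-typed

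*Protocol*

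**What the plan says.** The Objectives section sets two separate prevalence estimates, one for rectal screening isolates and one for clinical isolates: "To estimate the prevalence of clinical isolates from ICU patients that are positive for carbapenemase-producing Enterobacterales". The Aim covers infections and colonisations.

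In Appendix 1, the patient-level table holds the specimen data in a block called Microbiology details. Specimen type is asked once ("Was it a screening or clinical specimen"), with the response format "Single select drop-down: Screening Clinical Unknown". There is one collection date, with the instruction "If multiple specimens, please provide the most recent date", one laboratory number, one anatomical site and one organism field, described as "Organism isolated associated with CPE positive result". None of these fields carries a repeat note. The antimicrobial fields of the same table do: "NOTE: Field repeated up to 5 times depending on the specified number of antimicrobials taken".

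The table opens with a different selection rule. The date of interest, to which the exposure questions relate, is the date of the single screen if there is only one. With several screens the rule is "If any positive, date of first positive screen", otherwise the most recent screen. If the patient was never screened it is the survey day.

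Other fields also bear on CPE status. The Screening block records the trust admission screen, the ICU admission screen with date and result, status known on admission, and a 12-month history (Previous CPE) split into colonised and infected. The section Information collected expects linkage to the laboratory surveillance system for microbiology results, and adds: "All data that can be obtained via reliable data linkage has already been excluded from the Point Prevalence Survey questions".

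**The concern.** Several specimens per patient are expected. The unit-level form lists weekly screening as an option, the date-of-interest rule provides for multiple screens, and Study design includes both routine clinical samples and rectal screens. A single-entry block that asks for the latest specimen cannot hold that history.

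The patients most likely to have several specimens are those who stay long, are screened weekly or are being investigated for infection. It is plausible that these are also the patients in whom CPE is found. Losses would then fall on the numerator more than on the sample as a whole, and they would affect the survey's main outcome. Within one record, exposures may also be dated from one test while the specimen details describe another, which weakens the risk-factor analysis.

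**Working it through.** **Step 1. The two rules side by side.** Date of interest: screens only; first positive if any is positive, otherwise the latest. Microbiology block: screening or clinical; the date of the latest specimen, whatever its result. They agree when a patient has one screen and nothing else, or when all specimens are screens and all are negative. They can differ once a positive is followed by another specimen, or when a clinical specimen is the latest.

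**Step 2. Four patients traced through the form.**

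- *Negative admission screen, positive weekly screen, later negative weekly screen.* The date of interest is the positive screen and the block date is the last screen. The organism entry is either that nothing was isolated (the positive leaves the block) or the earlier organism (entered against the wrong specimen).
- *Positive clinical specimen, then a single negative screen.* The type is screening and the clinical positive leaves the block. The date of interest is that same negative screen, so the two dates match and show no trace of the positive.
- *Positive ICU admission screen, then a clinical specimen.* The type is clinical. The screen leaves the block but is kept in the ICU admission-screen field.
- *Positive on both types.* Only the later one can be entered in the block, so the other type loses a positive.

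**Step 3. What other fields recover.** The third case is recovered. The first and second are recovered only if staff apply Previous CPE to the whole period up to the survey, or if linkage supplies the result. Previous CPE gives no specimen type or organism, and its companion date is limited to results before the ICU admission screen. In the fourth case, the missing type is recovered only if it was an admission screen or is linked. The Data analysis section does not say which source defines a positive.

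**Step 4. Sample sizes, to set the scale.** The plan's figures reproduce with n = 2·N·p(1−p) / [(d²/z²)(N−1) + p(1−p)], using design effect 2, z = 1.96, N = beds and p = 1%, rounded up and then multiplied by 1.1.

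- Adults, N = 4090, d = 1%: 696.06, so 697 × 1.1 = 766.7 (stated 767).
- Paediatrics, N = 312, d = 2%: 146.10, so 147 × 1.1 = 161.7 (stated 162).
- Neonates, N = 1441, d = 1%: 602.12, so 603 × 1.1 = 663.3 (stated 664).

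Expected positives at 1% are 7.67, 1.62 and 6.64.

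**Step 5. Illustration.** The documents give no rate of multiple specimens. Let q be the share of positives displaced and not recovered (assumed). Positives kept = n × 1% × (1 − q); apparent prevalence = 1% × (1 − q).

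| q | Adults | Paediatrics | Neonates | Apparent prevalence |
|---|---|---|---|---|
| 10% | 6.9 | 1.5 | 6.0 | 0.90% |
| 25% | 5.8 | 1.2 | 5.0 | 0.75% |
| 50% | 3.8 | 0.8 | 3.3 | 0.50% |

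For completeness by type, suppose a share b of tested patients has both types and either is equally likely to be the latest. The block then omits the screening result for b/2 of tested patients and the clinical result for another b/2. With b from 20% to 80% (assumed), that is 10% to 40% for each type.

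**The case against.** The strongest reply is that the block is not the whole form. The Screening block holds both admission-screen results, and Previous CPE is anchored to the survey, not to admission. Read literally, it would capture any known positive from earlier in the stay. This stands, with the limits given in step 3.

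The most-recent instruction sits on the date field only. The organism field asks about a positive result, and the table's opening tells staff to answer in relation to the date of interest. So overwriting is one reading of conflicting instructions, not what the form prescribes. This also stands, but the other reading attaches the positive to the wrong date and possibly the wrong type, and trusts may choose differently.

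A recorded negative screen dated after the date of interest implies an earlier positive screen, because otherwise the two dates would match. That helps for screens, but not for clinical specimens or pending results.

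A reader might infer that linkage is ruled out, because reliably linkable items were taken off the form. The documents do not support this. The sentence before it names the laboratory system as a source of additional data, and the form collects NHS and specimen numbers. What remains is that linkage is only anticipated and is not assigned to the outcome.

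A reader might also infer that the rule in the section on laboratory specimens turns an overwritten positive into a negative. That rule covers patients with no CPE result. A patient with an earlier positive has one, and patients counted as negative stay in the denominator.

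**Conclusion.** The concern holds for the Microbiology details block. It conflicts with the date-of-interest rule, cannot hold both specimen types for one patient, and can displace or mis-type a clinical positive or a positive non-admission screen that is followed by another specimen. Type-specific prevalence can then be incomplete and biased downward for patients with more than one specimen, unless an unnamed second source recovers the case.

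A reader might go further and say that the two prevalences cannot be estimated separately. The documents do not support that: each recorded specimen is labelled by type, admission-screen results are kept elsewhere and linkage is anticipated. Nor is every patient with several specimens misrecorded; repeated negatives of one type do no harm.

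The amount of bias is unknown. With 767 × 0.5% = 3.8 to 767 × 1% = 7.7 adult positives expected, one unrecovered loss is 1/3.8 = 26% to 1/7.7 = 13% of the numerator. That only restates how few positives there are and is not an estimate of loss. The 0.90%, 0.75% and 0.50% figures rest on assumed displacement with no recovery. No sample-size figure changes.

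**What to change.** In Appendix 1, split the Microbiology details block into a screening entry and a clinical entry, each opening with tested yes/no. Use one selection rule in both, consistent with the date of interest: the first positive if any is positive, otherwise the most recent. Tie date, type, site, organism and carbapenemase family to that same specimen.

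Add to the clinical entry the colonised/infected choice already used for Previous CPE, since the specimen block has no such field and the Aim covers both states.

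In Data analysis, state whether the block, the Screening fields or the linked laboratory record defines a positive for each objective, and which prevails if they disagree.

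The cost is a few extra fields in the online tool and the printable form, mostly for patients with both specimen types, and one or two sentences of protocol text. No additional samples are needed.
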